16.1 Sample size calculation

Part 1

As no formal hypothesis testing will be conducted in Part 1, no formal sample size calculation is deemed necessary. In previous protocol versions, a pooling of p-values of Part 1 and Part 2 was planned and a sample size of N = 200 enrolled patients (100 per group) was calculated. It is assumed that with the previously planned sample size a robust estimation of all efficacy and safety parameters can be conducted. Thus, no adaptations in sample size for Part 1 are necessary.

Previously, the following assumptions were made:

3-stage group sequential adaptive test design with O'Brien and Fleming shaped boundaries

Information rate for Part 1 analysis: 0.2

O'Brien and Fleming alpha level for end of Phase 2 analysis: <0.0001

Primary endpoint: Proportion of patients without any need for invasive ventilation

Randomization ratio: 1:1 (45 mg/day IMU-838:placebo)

Power: 80%

Global significance level: 0.05, 1-sided

Proportions of patients with need for INV

for 45 mg/day IMU-838:	32%
for placebo:	40%
Number of patients (Part 1):	188

Considering a 6% drop-out rate, a total of 200 patients (100 per group) were to be enrolled.

Part 2

If the trial is expanded to Part 2, the sample size of Part 2 will be determined based on the results of MA1.

The Part 2 (Phase 3, Expansion Phase) trial will be designed to keep a global 1-sided alpha level of 0.025 (one-sided). A 2-stage group sequential test adaptive design with O'Brien and Fleming shaped boundaries will be used. Stage 1 will be IA2 applying an overall information rate of 50% and using an alpha of 0.0026. The use of group sequential boundaries within the context of an adaptive design is enabled using the inverse normal method, combining the p-values of both stages with weights based on the sample sizes. Statistical analysis methods that control for the Type I error will be used.

16.2 Analysis sets and types of analyses

Safety analysis set

The safety analysis set (SAF) will consist of all randomized patients who received at least one dose of IMP, i.e., any dose of IMU-838 or placebo. If it is uncertain if the patient has received any IMP, the patient will be included in the SAF. The analyses based on the SAF will be conducted on an “as treated” basis, i.e., all patients will be analyzed by the treatment they received.

Full analysis set

The full analysis set (FAS) will consist of all randomized patients who received at least one dose of IMP, i.e., any dose of IMU-838 or placebo. The analyses based on the FAS will be conducted on an intention-to-treat procedure, i.e., all patients will be analyzed by the groups to which they were randomized to.

Per-protocol set

All patients of the FAS will also be included in a per-protocol (PP) set if they did not violate any major protocol criteria. Protocol deviations will be identified and classified for each patient during a blind data review.

Assignment of analysis sets to analyses and allocation of patients

All efficacy analyses will be based on the FAS. The primary and the key secondary efficacy endpoints only will be additionally analyzed for the PP set. The analysis of the primary and the key

secondary efficacy endpoints using the FAS will be considered the primary analysis. All other analyses will be exploratory. Safety analyses will be based on the SAF.

The allocation of patients to the analysis sets for the final analysis will be done during a blind data review meeting.

16.3 Statistical analyses

16.3.1 General approaches

For qualitative variables, the frequencies (absolute and relative) will be calculated. Quantitative parameters will be described by declaring the mean value, standard deviation, minimum, first quartile, median, third quartile, and maximum. The treatment groups will be separately tabulated. A detailed description of the statistical analyses for all scheduled analyses (i.e., early safety analysis, MA1 and FA1, and interim and FA2) will be provided in a statistical analysis plan and will be finalized before the respective data (e.g. MA1/FA1, IA2, FA2) will be analyzed.

In Part 1, all endpoints will be analyzed descriptively. In addition, exploratory confidence intervals will be calculated for the primary and key secondary endpoints (and for other endpoints as appropriate) using an alpha of 0.1 (2-sided). No formal statistical tests will be conducted.

The Part 2 (Phase 3 Expansion Phase) trial will be designed to keep a global 1-sided alpha level of 0.025 (1-sided). A 2-stage group sequential test adaptive design with O'Brien and Fleming shaped boundaries will be used. Stage 1 will be the IA applying an overall information rate of 50% and using an alpha of 0.0026. The use of group sequential boundaries within the context of an adaptive design is enabled using the inverse normal method, combining the p-values of both stages with weights based on the sample sizes. Statistical analysis methods that control for the Type I error will be used.

In Part 2, the primary and key secondary endpoints will be tested confirmatory. Results of other endpoints will be considered exploratory, even when statistical tests are performed.

Confirmatory hypothesis testing of key secondary endpoints will be done only after the test of the primary efficacy endpoint was significant. Testing will be done strictly hierarchically in the given order to ensure the family wise error rate. Confirmatory hypothesis testing in the pre-defined order will stop once the first non-significant test result is obtained.

The FAS (all randomized patients who received at least one dose of IMP; as randomized) will be the primary analysis population. The PP analysis set and the set of only surviving patients until EoS will be applied as secondary/sensitivity analysis for the primary and key secondary endpoints, if applicable.

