15. Patients with pre-existing end-stage liver disease (Child Pugh B and C score)
16. Patients with known Gilbert syndrome (unless their indirect [unconjugated] bilirubin level is confirmed to be <1.2 x ULN, i.e. <1.1 mg/dL)
17. Patients with known acute or clinically relevant chronic renal failure, patients currently on dialysis, as well as patients with an estimated glomerular filtration rate value <30 mL/min/1.73 m² body surface area according to the Chronic Kidney Disease Epidemiology Collaboration equation for adults (or the Schwartz bedside equation for children and adolescents, if applicable)
18. History or presence of serious or acute heart disease such as uncontrolled cardiac dysrhythmia or arrhythmia, uncontrolled angina pectoris, cardiomyopathy, or uncontrolled congestive heart failure (New York Heart Association [NYHA] class 3 or 4)

Note: NYHA class 3: Cardiac disease resulting in marked limitation of physical activity. Patients are comfortable at rest. Less than ordinary activity causes fatigue, palpitation, dyspnea, or anginal pain. NYHA class 4: Cardiac disease resulting in inability to carry on any physical activity without discomfort. Symptoms of heart failure or the anginal syndrome may be present even at rest. If any physical activity is undertaken, discomfort is increased.

19. Legal incapacity, limited legal capacity, or any other condition that makes the patient unable to provide consent for the trial
20. Pregnant or breastfeeding
21. An employee of an investigator or Sponsor or an immediate relative of an investigator or Sponsor
22. Patients institutionalized due to judicial order

Statistical methods

Part 1

All endpoints will be analyzed descriptively. In addition, exploratory confidence intervals will be calculated for the primary and key secondary endpoints (and for other endpoints as appropriate) using an alpha of 0.1 (2-sided). No formal statistical tests will be conducted. The primary analysis will be based on the full analysis set (all randomized patients who received at least one dose of IMP as randomized). Secondary/sensitivity analyses may be performed using the per-protocol analysis set and the set of only surviving patients until EoS and will be further specified in the statistical analysis plan.

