Efficacy (continued)	
 • Proportion of patients 
 • with auxiliary oxygen therapy* (including all types of oxygen therapy) until Days 6, 14, and 28 • with clinical recovery defined as 
 • Axillary temperature ≤ 36.6 °C, or oral temperature ≤ 37.2 °C, or rectal or tympanic temperature ≤ 37.8 °C; and • Respiratory frequency ≤ 24 times/min without oxygen inhalation; and • Oxygen saturation $\geq 98\%$ without oxygen inhalation • With clinical improvement, defined as an improvement of at least 2 points on the WHO 9 category ordinal scale [21], or live discharge from hospital without oxygen supplementation, whichever comes first • Change in daily clinical patient status on the WHO 9-category ordinal scale [21] • Duration of INV • Duration of ECMO • Duration of RRT • Duration of auxiliary oxygen therapy (including all types of oxygen therapy) • Duration of hospitalization for survivors • Rate of ICU* admission until Days 6, 14, and 28 • Hospital-free days

Trial objectives and endpoints (continued)

Objective	Endpoint
Secondary (continued)	
Efficacy (continued)	
	
 • Time from IMP treatment initiation to death • Time to first prescription of INV • Time to first prescription of RRT • Time to first prescription of ECMO • Time to first prescription of INV, RRT, and ECMO • Time to ICU admission • Cumulative dose of vasoactive therapies and days (daily until Day 14) with vasoactive therapies (until Day 14) • Time to clinical recovery
Pharmacokinetics	
To evaluate trough plasma levels of IMU-838	
 • Morning trough plasma levels of IMU-838 on Days 0, 1 through 6, 14, and 28 • Correlation of trough levels (quartiles) to selected clinical outcomes
Safety	
To evaluate safety and tolerability of IMU-838	
 • AEs and SAEs • Vital signs • Clinical laboratory parameters (blood chemistry, hematology, and urinalysis) • Electrocardiogram (ECG) parameters • Temperature

Trial objectives and endpoints (continued)

Objective	Endpoint
Secondary (continued)	
Disease markers	
To explore blood levels of disease markers	
 • D-dimer • Lactate dehydrogenase (LDH) • C-reactive protein (CRP) • Troponin I (cTn) • Procalcitonin (PCT) • Correlation of disease markers to selected clinical outcomes

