16.3.2 Primary and key secondary efficacy endpoint analyses

In the following the analyses for the primary and key-secondary endpoints are described for Part 1. Since Part 1 and Part 2 will be independent parts, these endpoints may be changed for Part 2 after the MA1 analysis. More details and/or changes for evaluation in Part 2 will be specified in a protocol amendment and respective SAP when MA1 results are available.

Primary endpoint

The primary endpoint of the trial i.e., the proportion of patients without any need for INV until EoS. The “need for INV” (considered positive for the primary endpoint) will include patients:

1. placed on any INV method during the trial
2. who had an active “do not intubate” or “do not resuscitate” order established during the trial conduct or refused intubation for any reason but were assessed by the investigator to have a medical need for INV
3. who had a medical need for INV as assessed by the investigator but for reasons of medical resource exhaustion or due to triage decisions by the hospital had not received INV, or
4. who died mainly due to respiratory failure but had a need for INV as assessed by the investigator or before such needed INV could have been started

Patients who are lost to follow-up or discontinue the trial on or before Day 13 (last treatment day) due to any reason other than death and discontinue with a last observed WHO clinical status no lower than that at Screening, and patients who die and do not fall under Number 4 of the above-mentioned criteria will be considered treatment failures for the primary endpoint. A sensitivity analysis will be performed for patients who discontinued before EoS, using the available information on INV.

Invasive ventilation involves any instrument penetrating via the mouth (e.g., endotracheal tube), nose, or the skin (e.g., tracheostomy tube through a stoma) to serve as an artificial airway, and the manual or mechanical ventilation of the patient through such artificial airway.

For clarification, bilevel positive airway pressure (trademarked as BiPAP™ or VPAP™ by different manufacturers) and continuous positive airway pressure are not considered INV as they do not involve intubation. However, for classification of patient clinical status these methods are considered non-invasive ventilation (WHO Status 5, [Table 4](#)).

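### The survivors-only re-analysis in Section 16.3.1 is not a randomized comparison and cannot serve as a sensitivity check of the FAS result

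*Combined protocol and SAP*

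**What the plan says.** The synopsis (Section 1, Statistical methods, Part 1) and Section 16.3.1 both make the FAS the primary analysis population. Section 16.3.1 then adds the per-protocol set and a second set: "the set of only surviving patients until EoS will be applied as secondary/sensitivity analysis for the primary and key secondary endpoints", followed by the qualifier that this is done where applicable. The synopsis is softer: "Secondary/sensitivity analyses may be performed using the per-protocol analysis set and the set of only surviving patients until EoS", with detail left to the SAP.

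Section 16.2 defines the safety, full analysis and per-protocol sets only. On additional analyses it says: "The primary and the key secondary efficacy endpoints only will be additionally analyzed for the PP set". It does not mention a survivor set.

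The document does not say which endpoints the applicability qualifier removes, or how a patient of unknown vital status is assigned. Section 16.3.2 counts discontinued patients of unknown status as dead in the main mortality analysis and as alive in a sensitivity analysis, so membership of the set could follow either rule.

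In the FAS, death is kept as a bad outcome:
- **Primary endpoint (16.3.2):** deaths mainly from respiratory failure with a need for INV count as need for INV. For the rest, "patients who die and do not fall under Number 4 of the above-mentioned criteria will be considered treatment failures for the primary endpoint".
- **ICU duration (16.3.2):** deaths stay in, with the end date set to Day 28. One sensitivity analysis gives each death the full 28 days.
- **28-day all-cause mortality** is itself a key secondary endpoint.

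**The concern.** A sensitivity analysis asks the primary question again under different assumptions about data or model. Restricting to survivors changes the question. If the drug affects death, the two surviving groups differ in who is left, and randomization no longer makes them comparable.

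The direction is perverse. A drug that keeps ventilated patients alive adds ventilated patients to its own survivor group and looks worse. A drug that kills ventilated patients removes them and looks better. The restriction also reverses the plan's own rule that deaths are failures.

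For two key secondary endpoints the set loses its meaning. Mortality among survivors is 0% in both arms by construction, and survival without respiratory failure loses its survival component.

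At stake is interpretation. A survivor estimate reported beside the FAS estimate under a sensitivity label can seem to contradict or support it for reasons unrelated to robustness. Section 16.3.1 is not limited to Part 1, so the set could also be carried into Part 2.

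**Working it through.** **Inputs**
- Need for INV on placebo 40%, on IMU-838 32% (Section 16.1, earlier design assumptions).
- Activity thresholds on the primary endpoint: 20% relative (moderate) and 10% relative (mild, with a key secondary effect) (Section 16.4.2).
- Trial mortality: none assumed in the documents. Section 5.1 cites a general COVID-19 fatality of about 4-7%. The rates of 2-20% below are assumptions.

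**The plan's 20%.** From Section 16.1, (40 - 32)/40 = 20% on the need-for-INV scale. The Section 16.4.2 example instead gives the higher value to IMU-838 (40% against 32%). That fits the endpoint as defined, the proportion without need for INV. Both scales are therefore shown.

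**Formula.** Let F be the FAS failure proportion (need for INV or death) and D the proportion dead, all deaths being among failures. Then:
- INV-free among survivors = (1 - F)/(1 - D)
- need for INV among survivors = (F - D)/(1 - D)

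**No effect on failure: F = 40% in both arms, FAS odds ratio 1.00.** The survivor odds ratio is (40 - D placebo)/(40 - D drug), in percentage points. Relative differences are drug against placebo.

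| Deaths, placebo / drug | INV-free survivors, drug | INV-free survivors, placebo | Relative, INV-free | Relative, need for INV | Odds ratio |
|---|---|---|---|---|---|
| 10% / 5% | 60/95 = 63.2% | 60/90 = 66.7% | -5.3% | 36.8/33.3: +10.5% | 30/35 = 0.86 |
| 10% / 20% | 60/80 = 75.0% | 60/90 = 66.7% | +12.5% | 25.0/33.3: -25% | 30/20 = 1.50 |
| 5% / 2% | 60/98 = 61.2% | 60/95 = 63.2% | -3.1% | 38.8/36.8: +5.3% | 35/38 = 0.92 |

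The second row is a drug that doubles deaths. On the scale of the endpoint it appears 12.5% better, above the mild threshold of 10% and below the moderate one of 20%. The Section 16.4.2 examples divide by the IMU-838 value. On that convention the figure is (75.0 - 66.7)/75.0 = 11.1%, with the same conclusion.

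**With the design effect: F = 32% against 40%.** FAS odds ratio = (68/32)/(60/40) = 1.42. Survivor odds ratio:
- deaths 5% placebo, 2% drug: (68/30)/(60/35) = 1.32
- deaths 10% placebo, 5% drug: (68/27)/(60/30) = 1.26
- deaths 20% placebo, 5% drug: (68/27)/(60/20) = 0.84, reversed

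**A worse drug: F = 44% against 40%.** FAS odds ratio = (56/44)/(60/40) = 0.85. With deaths of 15% on drug and 5% on placebo, the survivor odds ratio is (56/29)/(60/35) = 1.13, reversed.

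**The case against.** The case for leaving the text alone has real substance.

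- **It is secondary and hedged.** Section 16.2 makes the FAS analysis primary and everything else exploratory. Part 1 has no formal tests. The applicability qualifier could exclude mortality, and the SAP is to settle details before the data are analyzed. This stands and limits the weight. But the qualifier is never explained, and the difficulty is not confined to mortality.
- **The mortality contrasts are assumed.** This also stands. Near the fatality cited in Section 5.1 the shift is small, and the reversals need much higher mortality and large differences between arms.
- **A rise in deaths would be seen.** 28-day mortality is among the Section 16.4.2 endpoints, and a consistent overall pattern is required. That makes it unlikely that a survivor result would mislead alone.
- **Much of the remedy exists.** Deaths are already failures for the primary endpoint, and one ICU sensitivity analysis already assigns them 28 days. The change is therefore mainly a deletion.

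A reader might infer that the survivor analysis could carry a harmful drug past the 20% moderate threshold and into Phase 3. The documents do not support that. The 25% figure arises only on the need-for-INV scale, whereas the endpoint and the Section 16.4.2 example are on the INV-free scale. Section 16.4.2 also never refers to the survivor set.

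A reader might also extend the point to "Duration of hospitalization for survivors" in Section 7. That is an ordinary secondary endpoint, listed alongside duration of hospitalization without that restriction and hospital-free days. It has the same weakness but lies outside this point.

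**Conclusion.** The point holds as one of analysis choice and labelling. A between-arm comparison in patients alive at EoS is not protected by randomization and should not be called a sensitivity analysis of the FAS result. That conclusion is structural and needs no mortality figure.

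The size does depend on mortality. With 40% failures in both arms and all deaths among them, the survivor odds ratio is 0.92 at 5% placebo against 2% drug mortality, 0.86 at 10% against 5%, and 1.50 at 10% against 20%, where the FAS gives 1.00.

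It would go too far to say that the primary result is biased: the FAS analysis retains deaths as failures. The activity decision is not tied to this set either. Section 16.4.2, however, does not name the analysis set for its thresholds or for the overall pattern it requires, and that gap is worth closing. Sections 16.2, 16.3.1 and the synopsis also disagree on whether the set is used at all.

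**What to change.** 1. In Section 16.3.1 and the synopsis, delete the survivors-only between-arm comparison for the primary and key secondary endpoints. Alternatively, limit it to description by arm with no between-arm estimate, and state that it does not apply to 28-day mortality or to survival without respiratory failure.
2. Reconcile Section 16.2. If a descriptive survivor set is kept, define it there, including how patients of unknown vital status are assigned.
3. State in Section 16.4.2 that the activity criteria use FAS results with deaths as failures.
4. Rely on what the plan already has: deaths as failures for the primary endpoint and the 28-day ICU value for deaths. Optionally, make the latter a worst-rank analysis. Under the preferred ICU rule, a patient who dies on Day 27 with no ICU stay is credited with only about one ICU day (28 - 27).

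The cost is wording in the protocol and SAP before the SAP is finalized, with no new data. One supplementary comparison is lost.

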16.3.2 Primary and key secondary efficacy endpoint analyses

In the following the analyses for the primary and key-secondary endpoints are described for Part 1. Since Part 1 and Part 2 will be independent parts, these endpoints may be changed for Part 2 after the MA1 analysis. More details and/or changes for evaluation in Part 2 will be specified in a protocol amendment and respective SAP when MA1 results are available.

Primary endpoint

The primary endpoint of the trial i.e., the proportion of patients without any need for INV until EoS. The “need for INV” (considered positive for the primary endpoint) will include patients:

1. placed on any INV method during the trial
2. who had an active “do not intubate” or “do not resuscitate” order established during the trial conduct or refused intubation for any reason but were assessed by the investigator to have a medical need for INV
3. who had a medical need for INV as assessed by the investigator but for reasons of medical resource exhaustion or due to triage decisions by the hospital had not received INV, or
4. who died mainly due to respiratory failure but had a need for INV as assessed by the investigator or before such needed INV could have been started

Patients who are lost to follow-up or discontinue the trial on or before Day 13 (last treatment day) due to any reason other than death and discontinue with a last observed WHO clinical status no lower than that at Screening, and patients who die and do not fall under Number 4 of the above-mentioned criteria will be considered treatment failures for the primary endpoint. A sensitivity analysis will be performed for patients who discontinued before EoS, using the available information on INV.

Invasive ventilation involves any instrument penetrating via the mouth (e.g., endotracheal tube), nose, or the skin (e.g., tracheostomy tube through a stoma) to serve as an artificial airway, and the manual or mechanical ventilation of the patient through such artificial airway.

For clarification, bilevel positive airway pressure (trademarked as BiPAP™ or VPAP™ by different manufacturers) and continuous positive airway pressure are not considered INV as they do not involve intubation. However, for classification of patient clinical status these methods are considered non-invasive ventilation (WHO Status 5, [Table 4](#)).

In Part 1, the primary endpoint will be displayed with frequency tables per stratification factor age (< or \geq 65 years) and antiviral therapy (no antivirals, Hydroxychloroquine and Chloroquine, all other antivirals) and overall. In addition, an odds ratio (OR) with an exact 2-sided 90% confidence interval will be conducted. The OR will be calculated adjusted for the stratification factors age (< or \geq 65 years) and antiviral therapy (no antivirals, Hydroxychloroquine and Chloroquine, all other antivirals).

Key secondary endpoints

Proportion of patients surviving without respiratory failure

Respiratory failure will be defined as the need of ICU, INV, high-flow oxygen or ECMO. Patients who are lost to follow-up or discontinue the trial on or before Day 13 (last treatment day) due to any reason other than death, and patients who discontinue with a last observed WHO clinical status no lower than that at Screening are considered respiratory failures. A sensitivity analysis will be performed for patients who discontinued before EoS, using the available information. Statistical analysis will follow the analysis of the primary endpoint.

Duration of ICU treatment until Day 28

The duration of ICU treatment until Day 28 will be analyzed in decimal days.

For patients who were transferred to ICU, the duration of ICU treatment will be calculated as [Time of discharge from ICU (date:hh:mm) - time of admission to ICU (date:hh:mm) + 1] / 1440. For patients who were discharged from ICU but readmitted the time from first admission until last discharge will be used. The time from investigator's decision to admit a patient to ICU until a patient is admitted will not be considered.

If the investigator decides that there is the medical need to admit a patient to the ICU but the patient is not admitted due to patient refusal, unavailability of ICU or due to rationing or triage decisions, the start time of ICU hospitalization will use the investigator's decision. The end of ICU duration will be imputed as Day 28 or, if ICU hospitalization occurs at a later study period, until end of actual ICU hospitalization.

The following imputation of concurrent events in the preferred analysis of ICU duration, creating the most conservative assessment approach will be performed: a) for all death cases that have no recorded or known ICU hospitalization in this trial, start date will be imputed as date/time of death, end date will be imputed as Day 28 b) if ICU treatment is known and started before the date of death, start date will be the actual ICU submission, end date will be imputed as Day 28.

For patients who are lost to follow-up or discontinue the trial on or before Day 13 (last treatment day) due to any reason other than death and patients who discontinue with a last observed WHO clinical status no lower than that at Screening, the following approach will be performed: a) for cases that have no recorded or known ICU hospitalization in this trial, start date will be imputed as date/time of discontinuation, end date will be imputed as Day 28 b) if ICU treatment is known and started before the date of study discontinuation, start date will be imputed as actual ICU submission, end date will be imputed as Day 28.

As sensitivity analyses, ICU duration imputation on available data will be done as follows:

- for patients who died, the study period of 28 days will be recorded as ICU treatment duration,
- for patients who discontinued the study prematurely or for patients who died before EoS, the available information on ICU treatment duration until day of discontinuation will be used.

In Part 1, the ICU duration will be displayed with basic statistics per stratification factor age (< or \geq 65 years) and antiviral therapy (no antivirals, Hydroxychloroquine and Chloroquine, all other antivirals) and overall. In addition, an exact 2-sided 90% confidence interval for the median of differences between treatment groups (location shift) will be conducted adjusted for the stratification factors age and antiviral therapy.

28-day all-cause mortality

28-day all-cause mortality will be derived as percentage of patients who died due to any cause from time of 1st IMP administration until EoS. In Part 1, 28-day all-cause mortality will be displayed with frequency tables per stratification factor age (< or \geq 65 years) and antiviral therapy (no antivirals, Hydroxychloroquine and Chloroquine, all other antivirals) and overall. In addition, an OR with exact 2-sided 90% confidence interval will be conducted. The OR will be calculated adjusted for the stratification factors.

Patients who discontinued the trial before Day 28 due to any other reason than death will be considered as deaths, unless survival status can be obtained by the investigator through other means (see Section [12.4](#)).

In a sensitivity analysis, patients who discontinued before EoS due to reasons other than death, will be considered as survived, unless the investigator has any information of patient death after discontinuation.

In Part 2, the primary endpoint (as selected during MA1) and the key secondary endpoints that include proportion of patients (e.g. patients without respiratory failure, 28-day all-cause mortality) will be evaluated for superiority of IMU-838 vs placebo with an exact Cochran-Mantel-Haenszel test, adjusted for the stratification factors age and antiviral therapy. In addition, logistic regression analyses will be conducted including the covariates age, antiviral therapy, sex, and country. The distribution of primary endpoint or any key secondary endpoint containing duration measurements (e.g. duration of ICU treatment) will be analyzed with the van Elteren test (stratified by age and antiviral therapy). In addition, time-to-event analyses using Kaplan Meier methodology and a stratified log rank test (stratification factors age and antiviral therapy) will also be performed. All tests will be performed 1-sided keeping a global alpha level of 0.025 (1-sided).

